## Long-term Follow-up

Patients will be followed periodically every 6 months (+/- 3 months) for survival via brief phone call, even after being taken off treatment. This may be done over the phone with a member of the study staff. The phone call should last about 10 minutes.

#### **VII. STUDY END POINTS**

#### **Primary:**

1. Response rate achieved with the chemotherapy regimen

## Secondary:

- 1. Event free survival at 2 years (events defined as death and relapses)
- 2. Overall survival
- 3. Remission duration
- 4. Predictive factors for response and outcome
- 5. Safety profile

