Patients, who have not achieved a complete remission (CR)/complete remission without platelet (CRi) recovery following one induction course can receive a second induction course to optimize response if possible. A second induction course at the same dose as the previous course or in a dose-reduced fashion should not be given until at least 28 days of course 1. If the bone marrow aspirate and/or biopsy(s) performed after the reinduction cycle reveals a remission marrow (CR/CRi), then the patient may proceed with consolidation at the discretion of the treating investigator. In addition, any clinically significant drug-related, non-hematologic toxicity experienced by a patient should return to ≤ grade 2 or the baseline grade before the patient continues treatment. Should the patient not have achieved a remission, including CR and CRi after the re-induction course, he/she will be taken off study for failure to respond, unless the patient has

achieved clinical benefit or partial remission, at which time further therapy on protocol may be permitted with approval from the PI.

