#### VIII. CRITERIA FOR WITHDRAWAL

#### Reasons for withdrawal include:

- Withdrawal of consent or the subject refuses to continue treatment and/or procedures/observations.
- Relapse unless the treating physician determines that the patient has achieved clinical benefit, at which time further therapy on protocol may be permitted with approval from the PI.
- Failure to achieve at least a CRi after 2 induction courses

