## Partial response (PR):

• Platelet count ≥ 100 ×10^9/L

• ≥ 50% reduction in bone marrow blasts over baseline

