## Relapse:

Increase of bone marrow blasts to > 10% after an initial response.

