## **XI. STATISTICAL CONSIDERATIONS**

This is a Phase II study of clofarabine, idarubicin, cytarabine, vincristine, and corticosteroids for patients with newly diagnosed or relapsed/refractory mixed phenotype acute leukemia

The primary objective is to evaluate the efficacy, with primary endpoint of response (CR or CRi) during a 2 month window. The two groups of patients will be evaluated separately; however accrual to both groups will be concurrent.

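### Event-free survival counts only death and relapse, so a patient who never responds has no event before death and induction failure is missed

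*Combined protocol and SAP*

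**What the plan says.** Section VII (Study End Points, Secondary) lists "Event free survival at 2 years (events defined as death and relapses" and closes the event list there. Section IX defines relapse as "Increase of bone marrow blasts to > 10% after an initial response".

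The plan recognises failure to respond, but only as a reason for leaving the study. Section V.2 (Induction) says that a patient without remission after re-induction, absent an approved exception for partial remission or clinical benefit, "he/she will be taken off study for failure to respond". Section VIII lists "Failure to achieve at least a CRi after 2 induction courses" among the reasons for withdrawal. Under Long-term Follow-up in Section VI, patients are then followed "for survival via brief phone call, even after being taken off treatment".

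Section XI names the "primary endpoint of response (CR or CRi) during a 2 month window" but gives no EFS estimator, time origin or censoring rule. Kaplan-Meier appears only in Part II, for survival in the relapsed cohort.

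**The concern.** Event-free survival is a named secondary objective in Section I. A reader of a 2-year EFS rate for an induction regimen will expect refractory disease to count against it. As defined here, a patient whose leukemia never responds carries no event until death. If later off-study treatment keeps that patient alive to 2 years, the survival is credited to this regimen. The error has one direction: the reported rate is either unchanged or too favourable. Even if every such patient dies within 2 years, the earlier part of the curve is too high, because the failure is dated at death and not when induction failed.

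**Working it through.** **Definitions.** The event list is {death, relapse}. Relapse needs a prior response. A patient with no response therefore has the event list {death}. Sections V.2, VI (Long-term Follow-up), VIII, IX and XI contain no rule that adds induction failure to EFS.

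This applies strictly to patients who never respond. Section IX does not restrict the initial response to CR/CRi. Patients with a partial response ("50% reduction in bone marrow blasts over baseline" plus a platelet criterion), with clinical benefit, or with a first CR/CRi after the 2-month window may later be scored as relapsing. The figures below use everyone without CR/CRi and are therefore upper bounds.

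**Inputs.** The plan states no EFS figure to reproduce.
- r, the CR/CRi rate: 70% anticipated and 50% historical (Section XI, 1.1). N = 40 newly diagnosed patients at most.
- Patients without CR/CRi: 40 x 0.30 = 12, or 40 x 0.50 = 20.
- s, 2-year survival of patients without CR/CRi, early deaths included: not in the documents; assumed 0-40%.
- e, responders' event-free probability (in the censoring reading, from off-study to 2 years): not in the documents; assumed 20-60%.

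**Literal reading** (follow-up for death continues after treatment stops).
- As written: EFS = r x e + (1 - r) x s.
- With induction failure counted: EFS = r x e.
- Difference: (1 - r) x s.

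| | r = 70% | r = 50% |
|---|---|---|
| s = 0 | 0 points | 0 points |
| s = 40% | 0.30 x 0.40 = 12 points (12 x 0.40 = 4.8 of 40 patients) | 0.50 x 0.40 = 20 points (20 x 0.40 = 8 of 40) |
| Stand-in, s = 7.1% | 2.1 points (0.85 of 40) | 3.5 points (1.4 of 40) |

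The stand-in takes the 27.3-week median overall survival that the Rationale quotes for 20 de novo patients and assumes an exponential curve: s = 0.5^(104.4/27.3) = 0.071. That median is for all de novo patients in the series, not for non-responders.

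If half of the patients without CR/CRi were scored as relapsing by 2 years (assumed, with the same survival), the bounds halve: 0-6 and 0-10 points, or 1.1 and 1.8 points with the stand-in.

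**Censoring reading** (non-responders censored when taken off study, Kaplan-Meier used). With no early deaths, the estimate is e if failures are censored and r x e if they are counted. The difference is (1 - r) x e, and early deaths make it smaller.
- r = 70%: 0.30 x 0.20 to 0.30 x 0.60 = 6 to 18 points at most.
- r = 50%: 0.50 x 0.20 to 0.50 x 0.60 = 10 to 30 points at most.

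**Timing against the 2-month window.** A second course "should not be given until at least 28 days of course 1". The induction marrow is due on day 28 +/- 7.
- Second course at day 28: its marrow falls on day 28 + 21 to 28 + 35 = day 49 to 63.
- Second course at day 35: day 56 to 70.
- Two months is 60.9 days, so a permitted second-course assessment can fall outside the window.

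**The case against.** The strongest reply is that little is lost. A non-responder's death is still an EFS event, so if all such patients die within 2 years the 2-year rate does not move. The primary endpoint counts every induction failure, and the CR/CRi rate will be reported beside EFS. EFS is one of five secondary endpoints, with no hypothesis, target or stopping rule. The event list is stated openly. The size rests on assumed s and e, and the one scenario tied to a documented survival figure amounts to about one patient in 40. The largest figures need a censoring rule that no section states, and continued survival follow-up points away from it.

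Most of this stands as a limit on importance. The 6-30 point range shows what an unstated rule could do; it does not predict what will happen. It does not rescue the definition: neither reading counts the failure, and nothing restricts EFS to responders. If that restriction was intended, the measure would overlap with remission duration, which is a separate endpoint in the same list.

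Two further objections bear on the remedy. Dating failure at the post-induction assessment leaves open the living patient who has none. It also scores as failed a partial responder who continues on protocol and later reaches CR. Both are choices, and the plan should make them explicitly.

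**Conclusion.** The concern holds. The closed event list and the conditional definition of relapse together leave induction failure out of EFS for patients who never respond. Relative to an EFS that counts it, the 2-year rate is biased upward or not at all.

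On the literal reading the excess is at most 0-12 points at 70% response and 0-20 points at 50%, for assumed s of 0-40%, and about 2 and 4 points with the 27.3-week stand-in. On the censoring reading it is at most 6-18 and 10-30 points, for assumed e of 20-60%. The textual finding is firm; the size is not, because the documents give neither s nor e. No size is claimed for the relapsed cohort, for which Part II states no response rate. The definition should be corrected before EFS is analysed, but the primary endpoint and the monitoring rules do not depend on it.

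**What to change.** In Section VII, define EFS events as death from any cause, relapse after CR/CRi, or failure to achieve CR/CRi after the last induction course given (up to two). Then:

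- Date the failure at the response assessment that follows that course (marrow, blood counts and any extramedullary site), whether or not the patient stays on protocol.
- Cover patients who stop after one course, since Section VIII classifies failure only after two.
- State the time origin and the censoring rule, including how a living patient without a post-induction assessment is handled.
- Say whether a first CR/CRi found at a second-course assessment after the 2-month window counts as a response, and treat it the same way in EFS.
- Keep overall survival as the separate endpoint that includes the effect of later therapy.

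The cost is a short amendment to the definition and a few sentences in Section XI. Induction marrows and blood counts are already scheduled in Section VI, so no new procedure is needed. The reported EFS will be somewhat less favourable.

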#### VIII. CRITERIA FOR WITHDRAWAL

#### Reasons for withdrawal include:

- Withdrawal of consent or the subject refuses to continue treatment and/or procedures/observations.
- Relapse unless the treating physician determines that the patient has achieved clinical benefit, at which time further therapy on protocol may be permitted with approval from the PI.
- Failure to achieve at least a CRi after 2 induction courses

## IX. CRITERIA FOR RESPONSE

The response criteria recommended by the NCI and the MDS International Working Group.

#### **Definitions:**

# Complete Response (CR):

- Neutrophil count ≥ 1.0 ×10^9/L
- Platelet count ≥ 100 ×10^9/L
- Bone marrow aspirate < 5% blasts
- No extramedullary leukemia

#### CRi:

Response as in CR but platelets <100 ×10^9/L

## Partial response (PR):

• Platelet count ≥ 100 ×10^9/L

• ≥ 50% reduction in bone marrow blasts over baseline

## **Clinical benefit:**

In addition to IWG criteria, in AML, a decrease in bone marrow blasts to <5% will also be considered clinical benefit.

#### **Stable Disease:**

In addition to IWG criteria and in absence of any of the above response criteria, patients will be considered to have stable disease if the bone marrow blast percent does not increase compared to pretreatment level.

## Relapse:

Increase of bone marrow blasts to > 10% after an initial response.

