# IV. Eligibility Criteria

#### **Inclusion Criteria**

- 1. Sign an informed consent document
- 2. Age 18 >/= 18
- 3. Newly diagnosed or relapsed MPAL, which for this protocol, will be defined as follows:
- -Bone marrow result interpreted by the reading Pathologist (or tissue biopsy for cases of extramedullary disease) as: biphenotypic leukemia, bilineal leukemia, undifferentiated leukemia, mixed lineage leukemia, leukemia of ambiguous lineage, T/Myeloid leukemia, B/Myeloid leukemia, or other diagnosis indicating the presence of multiple lineages within the cell population.

Or

- -Immunophenotype consistent with WHO definition of MPAL
- 4. ECOG Performance Status of ≤ 3 at study entry.
- 5. Adequate organ function as outlined below (unless due to leukemia)
  - Serum creatinine ≤ 3 mg/dL
  - Total bilirubin ≤ 2.5 mg/dL
  - ALT (SGPT) and/or AST (SGOT) ≤ 3 x ULN or ≤ 5 x ULN if related to disease
- 6. Women of childbearing potential must have a negative serum or urine pregnancy test within 7 days. Women of childbearing potential and men must agree to use contraception at study entry and for the duration of active study treatment.
- Cardiac ejection fraction ≥ 40% (by either cardiac echo or MUGA scan).
   Documentation of recent (≤ 6 months from screening) outside reports is acceptable.
- 8. If newly diagnosed, prior therapy with hydrea and/or steroid and the use of a single or a two day dose of cytarabine (up to 3 g/m²), for emergency use up to 24 hours prior to start of study therapy is allowed.

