## 7. Maintenance Therapy

Maintenance or continuation chemotherapy for up to 3 years is the standard of care for ALL patients. Furthermore, one of the larger experiences in MPAL gave all patients continuation therapy for 2.5 years. Other series have not included maintenance therapy. Therefore, maintenance therapy after the completion of consolidation will be at the discretion of the managing physician. Targeted therapy will continue during maintenance per the managing physician.

Maintenance can be given for up to 30 months as follows:

- Vincristine 2 mg (FLAT dose) IV over 15 30 minutes once monthly
- Prednisone 200 mg (FLAT dose) PO daily for 5 days every month
- Methotrexate 20 mg/m^2 PO given once weekly
- 6-Mercaptopurine 50 mg PO three times daily

Doses can be adjusted as clinically warranted at the discretion of the managing physician. In every day clinical practice, doses of methotrexate and 6-mercaptopurine are reduced for myelo- or hepato-toxicity. Vincristine is dose-reduced or omitted for clinically significant peripheral neuropathy. Corticosteroids are dose-reduced or omitted

in patients with active infectious issues. All dose adjustments in maintenance will be captured by research personnel for analysis.

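### As written, 2-year EFS and remission duration can miss extramedullary relapses and relapses that occur after treatment ends

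*Combined protocol and SAP*

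**What the plan says.** All references are to the combined protocol and SAP.

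- **Endpoints.** Section VII names five secondary endpoints. They include EFS at 2 years, with deaths and relapses as the events, and remission duration.
- **Relapse.** Section IX gives one sentence: "Increase of bone marrow blasts to > 10% after an initial response".
- **Remission.** The CR definition in the same section includes "No extramedullary leukemia". CRi is CR with a lower platelet count, so it carries the same condition.
- **Eligibility.** Inclusion criterion 3 accepts a diagnosis by marrow, "or tissue biopsy for cases of extramedullary disease".
- **Outside criteria.** Section IX opens with "The response criteria recommended by the NCI and the MDS International Working Group" and gives no version and no order of precedence. Two later definitions say how they relate to those criteria: clinical benefit ("In addition to IWG criteria, in AML") and stable disease ("In addition to IWG criteria and in absence of any of the above response criteria"). The relapse definition does not.
- **Length of treatment.** Section V.3 allows up to 6 consolidation cycles at intervals of 3 to 10 weeks. Section V.7 says "maintenance therapy after the completion of consolidation will be at the discretion of the managing physician", for up to 30 months.
- **Follow-up.** In Section VI, exams and blood counts after remission are tied to treatment courses, and marrows are done as indicated. Under Long-term Follow-up: "Patients will be followed periodically every 6 months (+/- 3 months) for survival via brief phone call, even after being taken off treatment".
- **Analysis.** The Part I analysis plan covers descriptive statistics and the posterior response rate. Part II names Kaplan-Meier for survival in relapsed patients. Neither part gives a time origin, censoring rule or estimator for EFS or remission duration.

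**The concern.** Relapse can drop out of these endpoints by two separate routes.

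**Definition.** The conditions for entering remission cover the marrow and extramedullary sites. The written condition for relapse covers the marrow only. A responder with an isolated CNS or other extramedullary recurrence would no longer meet CR, yet would not have relapsed. This bears most directly on patients enrolled on a tissue biopsy, whose disease may return only at its original site.

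**Collection.** Once a patient stops treatment, no section calls for relapse status or date to be collected. A patient recorded only as alive may have relapsed.

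If such patients are carried as event-free until death or last contact, both endpoints are overstated. Under another censoring convention the bias could differ in size or direction, and the plan does not say which convention applies. For EFS, a later death turns many missed relapses into late events rather than lost ones. Remission duration has less protection, because a death does not supply the relapse date.

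**Working it through.** The plan states no expected rate, event count or precision for EFS or remission duration, so there is no planned figure to reproduce. The check is a reading of the text plus some bounding arithmetic.

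**1. One patient against the definitions.** Take a responder whose marrow blasts stay below 5% and who develops an isolated CNS recurrence.
- Under the CR definition, the extramedullary condition fails, so the patient is no longer in CR or CRi.
- Under the relapse sentence, marrow blasts do not exceed 10%, so there is no relapse.
- Under the EFS definition, there is neither death nor relapse, so there is no event.
- Under the cited NCI and IWG criteria, the result is unknown from the documents.

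**2. Can treatment end before 2 years (104 weeks)?**
- Six consolidation cycles take 6 × 3 = 18 to 6 × 10 = 60 weeks.
- The plan does not fix the length of induction. Assume 4 weeks per course and one or two courses.
- Shortest: 4 + 18 = 22 weeks. Longest: 8 + 60 = 68 weeks.
- Counting 2 years from the start of treatment (also an assumption), the period with survival calls only is 104 − 68 = 36 weeks to 104 − 22 = 82 weeks, or about 8 to 19 months.
- Fewer cycles lengthen this period. Thirty months of maintenance would close it.

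**3. Effect of one missed relapse on EFS (newly diagnosed group, maximum 40).**
- If the patient is alive and carried event-free at 2 years: 1/40 = 2.5 points.
- Allowing for death as an event, with an assumed 25% to 75% chance of being alive at 2 years: 2.5 × 0.25 = 0.6 to 2.5 × 0.75 = 1.9 points.
- Binomial standard error for an assumed EFS of 30% to 70%: √(0.3 × 0.7/40) = 7.2 points to √(0.5 × 0.5/40) = 7.9 points.
- Missed relapses of the full 2.5-point kind needed to equal one standard error: 7.2/2.5 = 2.9 to 7.9/2.5 = 3.2, so about three.

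**4. Remission duration.** This rests on responders only. At the response rates in Section XI, 1.1, there would be 0.5 × 40 = 20 to 0.7 × 40 = 28 of them. One uncollected relapse is then 1/28 = 3.6% to 1/20 = 5.0% of the group. That is a share of patients, not an effect on the estimate.

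**5. Dating.** If the call window is read as the interval between calls, calls are 6 − 3 = 3 to 6 + 3 = 9 months apart. A relapse noted without its date is located only to within that interval.

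**The case against.** The strongest case is that these endpoints are under-specified rather than wrong, and much of it stands.

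- **A reader might infer that extramedullary relapse is excluded.** The documents do not support that. Section IX invokes outside criteria, which may cover it and cannot be consulted here. Nor does it prove much that clinical benefit and stable disease are expressly additional to the IWG criteria while relapse is not: the CR, CRi and PR definitions lack that phrase too. What the text supports is that the governing definition is not stated.
- **Remission duration is less exposed on the definition.** An extramedullary recurrence breaks the CR or CRi condition, so remission can be read as ended whatever the relapse sentence says. That reading is reasonable, but the plan does not state it, and it does not create an EFS event.
- **A reader might infer that relapse is not captured at all.** That goes too far. During treatment, exams and counts precede each course, and relapse is a withdrawal reason in Section VIII. This is a single-center trial, so clinic records may catch some later relapses. What remains is patients who stop treatment and relapse afterwards, for whom collection is not planned.
- **The effect per patient is small**, and the survival range used above is assumed. This stands.
- **Other gaps exist.** Living induction failures are not EFS events as written, and marrow blasts of 5% to 10% meet neither the CR nor the relapse threshold. Both are separate questions, and the fix below does not settle them.

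**Conclusion.** The point holds in a limited form. Following the plan as written can leave an isolated extramedullary or CNS recurrence uncounted in EFS, unless the cited criteria supplement the relapse sentence. It can also leave relapse after treatment uncollected for both endpoints.

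It would be too strong to say that the two endpoints are unreliable. The number of affected patients cannot be derived, and EFS would shift materially only if several relapses were missed: about three patients alive and carried event-free at 2 years equal one standard error. That comparison assumes 40 newly diagnosed patients and a true EFS of 30% to 70%. Remission duration depends more on the relapse date and rests on fewer patients.

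The primary endpoint (CR or CRi in a 2-month window) and all stopping rules are unaffected. The missing time origin and estimator are gaps in detail and would not justify a finding alone. The change should be made because it is cheap and two of the five secondary endpoints depend on it. Confidence is medium, because the definition part turns on criteria that the documents cite but do not reproduce.

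**What to change.** 1. **Definition.** For EFS and remission duration, reconcile the opening reference, the CR definition and the relapse definition in Section IX into one stated relapse definition consistent with CR. Recurrence at an extramedullary site, including the CNS, after CR or CRi should count as an event alongside the existing marrow criterion. State how this endpoint definition relates to the word relapse in the withdrawal criteria (Section VIII), without changing clinical management.
2. **Collection.** At the existing six-monthly call, also record relapse status, date and site.
3. **Censoring.** Censor patients without relapse or death at the last contact at which relapse status was known, not at the last contact at which they were known to be alive.
4. **Supporting text.** State the time origin of each endpoint and name Kaplan-Meier as the estimator.

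The cost is one reconciled definition, one short analysis paragraph and one extra question on a call already planned, with no new visits or procedures. The downside is that reported EFS and remission duration may be slightly less favourable.
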